**b) Explain why human subjects must be used for this project.**

We are interested in improving human health using recommendations by American Diabetes Association with dairy protein supplementation and therefore need to use human subjects.

**c) Alternative Procedures. If the proposed study is a clinical trial of a drug, vaccine, device or treatment, describe alternative procedures, if any, that might be advantageous to the subject. Describe the important potential risks and benefits associated with the alternative procedure(s) or course(s) of treatment. Any standard treatment that is being withheld must be disclosed. This information must be included in the consent form.**

No alternative procedures

**d) If the proposed study is a clinical trial of a drug, vaccine, device or treatment, will it be possible to continue the more (most) appropriate therapy for the subject(s) after the conclusion of the study?**

Clinical parameters obtained during the study will be available to the participants to share with their primary physician. Then the subject and primary physician can decide on the most appropriate therapy for the subject after the conclusion of the study.

**e) Study Endpoint. If the proposed study is a clinical trial of a drug, vaccine, device or treatment, what are the guidelines or end points by which you can evaluate the alternative treatments during the study? If one treatment proves to be clearly more effective than another (or others) will the study be terminated before the projected total subject population has been enrolled? When will the study end if no important differences are detected?**

No alternative treatments

**f) State if deception will be used. If so, provide a rationale and describe debriefing procedures. Submit a**

**debriefing script in the Attachment Section (#16).**

No deception will be used.

**3. Background**

**a) Describe past experimental and/or clinical findings leading to the formulation of the study, if applicable.**

Physical activity and the biguanide drug Metformin have been shown independently to reduce the incidence of T2D. Interestingly, these data also suggest in adults over the age of 60 metformin had marginal efficacy while physical activity lowered incidence of T2D by 70%. Currently, governing agencies recommend physical activity and metformin together for individuals with pre-diabetes of all ages to prevent the progression to overt T2D. Until recently, the interaction between exercise and metformin has been largely understudied. Members of our investigative team have previously showed that metformin does not enhance but may blunt the glucoregulatory and cardiovascular response to acute and chronic exercise, which is especially relevant to older adults. A purported mechanism of action is that metformin inhibits mitochondrial respiration, which likely limits VO2max and mitochondrial protein synthesis. We have previously demonstrated that post-aerobic exercise dairy feeding can improve VO2max to a greater extent than post-exercise carbohydrate beverage. Therefore, we feel dairy supplementation may override the potential inhibition of metformin on exercise adaptations and maximize the benefits for older adults. To date, real-time continuous glucose monitoring is limited in individuals at risk of T2D. Moreover, glucose profiles via CGM during or in response to exercise, metformin and/or post-exercise nutrition have yet to be fully characterized. Much clinical research is limited to measurements in the clinical research setting while real-time glucose monitoring performed in both the standardized clinical research setting and in free-living scenarios is novelty of the current study design that will close a gap in knowledge regarding glucoregulatory effects of exercise, metformin and/or standardized post-exercise nutrition.

**b) Describe any animal experimentation and findings leading to the formulation of the study, if applicable.**

-----  
**\*\*\* Radioisotopes or Radiation Machines \*\*\***

You selected NO for Radioisotopes in the General Checklist. If you would like to add Radioisotopes, change the selection to YES in general Checklist.

**4.**

Radioisotopes or Radiation Machines Please note: For projects requiring radiation procedures, please contact the CSU Radiation Control Office (RCO). For more information see: <http://www.ehs.colostate.edu/WRad/Home.aspx> :

**a) If applicable, summarize in lay language the radiographic diagnostic and therapeutic procedures associated with this protocol.**

Body composition will be measured by dual energy x-ray absorptiometry (DEXA) before and after the 12 weeks of exercise in pre diabetic participants. In healthy individuals, one DEXA scan will be performed.

**b)** Are the radiation procedures being performed a normal part of the clinical management for the medical condition that is under study (Standard of Care) or are the procedures being performed because the research subject is participating in this project (extra CT scans, more fluoroscopy time, additional Nuclear Medicine Studies, etc.) (Not Standard of Care)? If some procedures are Standard of Care and some are Not Standard of Care, check both boxes.

**NOT STANDARD OF CARE**

If it is not standard of care, complete the rest of this section. Provide the CSU RCO approval information

X

**STANDARD OF CARE**

If it is only standard of care, skip the rest of this section.

CSU Radiation Control Office approved protocol number:

CSU Radiation Control Office protocol approval date:

For more information, see the RCO website at: <http://www.ehs.colostate.edu/Wrad/home.aspx> or Contact: [name], Radiation Safety Officer, at [contact].

-----  
**\*\*\* Medical Equipment for Human Subjects and Laboratory Animals; Investigatiional Devices \*\*\***

**5. Medical Equipment for Human Subjects**

If medical equipment is being used for human subjects/patients, describe this equipment and indicate if the use is normal practice for the population under study. You may have already described this equipment in the Study Procedures section. If you have already listed this information in the Study Procedures Section, please do not duplicate this information here. In the space below, input N/A if not applicable, indicate if this is already listed in the Study Procedures Section, or describe the equipment.

Continous Glucose Monitor (CGM) described in study procedures and in the attached investigator brochure and user guide. The Dexcom G6 CGM is for investigational use and is not FDA approved.

**6. Investigational Devices**

Please list in the space below all Investigational Devices to be used on Subjects.

**Investigational Devices**

**Investigational Devices**

**Describe the device(s) to be used**

DEXCOM G6 Continuous Glucose Monitoring (CGM) System. CGM can supplement, but does not replace, blood glucose monitoring. Previous versions of the device (Dexcom SEVEN PLUS, G4 PLATINUM, and G5 Mobile CGM) have been classified as a Class III device according to 21 CFR Part 814. The device's product code is MDS. Class III devices generally are those for which insufficient information exists to determine that general or special controls are sufficient to provide a reasonable assurance of safety and effectiveness.

**Device Name** DEXCOM G6 Continuous Glucose Monitoring (CGM) System  
**Manufacturer** Dexcom, Inc.

Significant risk Y Non-Significant risk

**IDE #**

**Rationale for Non-Significant Risk Device**

Device is not exempt from requirements in 21 CFR 812. Device is intended as an implant? Device is purported or represented to be for use supporting or sustaining human life? Device used of substantial importance in diagnosing, curing, mitigating, or treating disease, or otherwise preventing impairment of human health? Device presents a potential for serious risks to the health, safety, or welfare of a subject? If yes to any, then considered SR device.

If a non-significant risk device study is indicated, provide rationale for the device being non-significant risk. Please state if you need IRB guidance on whether this is a significant or non-significant risk device.

-----  
**\*\*\* Drugs, Reagents, or Chemicals \*\*\***

**7. Drugs, Reagents, or Chemicals**

- a) Please list in the space below all investigational drugs, reagents or chemicals to be administered to subjects during this study.
  
- b) Please list in the space below all commercial drugs, reagents or chemicals to be administered to subjects during this study.

Drug Name	Metformin
Source (e.g., Pharmacy, Sponsor, etc.,)	Pharmacy
If not premixed, where will the material be mixed and by whom	
Manufacturer	
IND # (if available)	
Dosage	Maximum dose of 1500 mg/day
Administration Route	Oral
N	Are these new or different uses of these commercially available drugs, reagents, or chemicals?
N	IND Regulations

**Please read the IND Statements**

-----  
**\*\*\* Subject Population (a-g) \*\*\***

8. Subject Population - In the space below, please detail the participants that you are requesting to recruit (include requested participant number and description of each group requested). (Input N/A if not applicable)
- a) **Requested Participant Description (Include number of participants that you plan to study and description of each group requested, if applicable).**

We plan to recruit 120 men and women with an estimation that 15-25% of participants will not qualify (i.e., screen out) and 15-25% of participants will not complete the study (i.e. drop out). We plan to complete the study in 60 men and women aged >55 years who are prediabetic defined as impaired fasting glucose (100 to 126 mg/dl), HbA1c (5.7-6.4%), family history of type 2 diabetes, and/or impaired glucose tolerance defined as 2 hour postprandial blood glucose of 140 to 200 mg/dl. Participants will be eligible if they meet any 1 of these criteria.

10 healthy individuals, 18-45 years old who have normal glucose values (fasting glucose (<100mg/dl), HbA1c (<5.7%), 2 hour postprandial blood glucose (<140mg/dl)) or no family history of type 2 diabetes will be recruited.

Sub-study: 20 pre diabetic participants and 10 healthy individuals will complete the study.  
Subpopulation of [xx] participants will be recruited for Physical Activity Behavior Counseling (previously approved in Amendment 3.

- b) **What is the rationale for studying the requested group(s) of participants?**

Individuals at risk for T2D are the intended population for metformin; CGM; and Counseling studies. We will use a healthy control group to compare to individuals at risk for T2D.

- c) **If applicable, state the rationale for involvement of potentially vulnerable subjects to be entered into the study, including minors, pregnant women, economically and educationally disadvantaged, or decisionally impaired subjects. Specify the measures being taken to minimize the risks and the chance of harm to the potentially vulnerable subjects.**

We will not enroll minors, pregnant women, economically and educationally disadvantaged, or decisionally impaired subjects.

- d) **If women, minorities, or minors are not included, a clear compelling rationale must be provided. Examples for not including minors: disease does not occur in children; drug or device would interfere with normal growth and development; etc.**

Minors are not included because the cost-benefit ratio is not clear and therefore inappropriate for this study.

- e) **State if any of the subjects are students, employees, or laboratory personnel. They should be presented with the same written informed consent. If compensation is allowed, they should also receive it.**

If any of the subjects are students, employees, or laboratory personnel they will be presented with the same written informed consent and compensation.

- f) **Describe how potential subjects will be identified for recruitment (e.g., chart review, referral from individual's treating physician, those individuals answering an ad). How will potential participants learn about the research and how will they be recruited (e.g., flyer, email, web posting, telephone, etc.)? Attach recruitment materials in the Attachment Section (#16). Important to remember: potential subjects may not be contacted before IRB approval.**

Potential subjects will be recruited initially from the Colorado State and Fort Collins community via email, electronic, newspaper, radio, or bulletin advertisements. Colorado State employees, local physicians and interested participants may be emailed for recruitment and communication purposes. Physicians will be contacted so if they have prediabetic patients they can be informed of the research study which includes standard care treatment options (i.e., physical activity and metformin). Text for advertisements will be obtained from the attached flyer. Information for local physicians is also attached.

- g) **If applicable, provide rationale for the inclusion of healthy volunteers in this study. Specify any risks to which these healthy volunteers may possibly be exposed. Specify the measures being taken to minimize the risks and the chance of harm to these volunteers.**

We will include healthy volunteers to compare to individuals at risk for T2D. No additional risks are known for healthy individuals compared to those at risk for T2D. Healthy individuals will not perform the intervention.

---

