**c) Proposed Start Date (may not precede IRB approval date):**

August 1, 2015

2.

Study Procedures (If this is a student project, the methods section of the thesis or dissertation proposal must be attached in section #16 - Attachment section.)

**a) In lay language, describe all the procedures, from screening through end-of-study, that the human subject must undergo in the research project, including study visits, drug treatments, randomization and the procedures that are part of standard of care. Please note: Do NOT respond "See Attachment Section." If you would like to add tables, charts, etc., attach those files in the Attachment section (#16).**

Study Overview:

Pre-diabetic and healthy participants will first undergo a medical questionnaire, resting ECG, graded exercise test with ECG and assessment of VO2max, anthropometric measurement (height, weight and body composition by DEXA scanning), an oral glucose tolerance test (OGTT), and a muscle biopsy.

Prediabetic participants will be screened to eliminate those lactose intolerant, medications known to affect the primary outcomes, medications or recent procedures contraindicated with metformin or not pre-diabetic. Subjects who meet these criteria will be randomized so that subject characteristics are matched between groups, while the study team and participants will remain blinded to treatment (i.e., randomized, double-blind study design). Subjects will be assigned to exercise + carbohydrate + placebo, exercise + protein + placebo, exercise + carbohydrate + metformin, or exercise + protein + metformin.

A minimum of two days apart from the VO2max test, skeletal muscle will be sampled from pre-diabetic and healthy participants. During these visits, pre-diabetic subjects will have the option to participate in a study to test the impact of one counseling session on physical activity after completion of the exercise training and to identify individual, socio-cultural and environmental determinants of physical activity 12 weeks after the end of the exercise intervention. If the subjects wish to participate they will complete questionnaires to measure sociodemographic information, physical activity, self-efficacy, planning, self-regulation and outcome expectancy of exercise, and perceptions of neighborhood support at baseline, completion of exercise training and 12 weeks after the exercise training.

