**Statistical Plan**

Data are presented as mean  $\pm$  standard error of the mean (SEM) and a significance was set a priori at  $P < 0.05$ . Normality was confirmed by the D'Agostino and Pearson test. A two-way ANOVA (Treatment Group x Time) with repeated measures for time was performed. Upon a significant effect, a Holm-Sidak's post-hoc test was used for multiple comparisons. When comparing the change ( $\Delta$ ) from pre to post-intervention between groups, data were analyzed using an unpaired t-test. Pearson's correlation coefficient ( $r$ ) was used to determine associations between dependent variables. GraphPad Prism 7.0 was used to perform statistical analysis

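### With 15–25% drop-out expected, the pre/post outcomes get an unadjusted completers-only analysis; a baseline-adjusted one by assigned arm removes baseline-related drop-out bias and is more precise

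*Combined protocol and SAP*

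**What the plan says.** Subject Population, item 8a, gives the planned attrition. Recruitment is set at 120 people, and a loss of 15–25% is allowed for at screening. For the period after that, the text expects that "15-25% of participants will not complete the study (i.e. drop out". The target is stated in completers: "We plan to complete the study in 60 men and women".

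Study Procedures, item 2a, sets out four arms: "Subjects will be assigned to exercise + carbohydrate + placebo, exercise + protein + placebo, exercise + carbohydrate + metformin, or exercise + protein + metformin". DEXA, VO2max, OGTT and the muscle sample are taken once before and once after the 12 weeks. Stable isotope incorporation is measured only afterwards.

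The Statistical Plan is one paragraph. Its main analysis reads: "A two-way ANOVA (Treatment Group x Time) with repeated measures for time was performed". Holm-Sidak comparisons follow a significant effect, and pre-to-post changes are compared between groups by an unpaired t-test. The plan names no analysis population, missing-data rule, baseline covariate or sensitivity analysis.

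**The concern.** With one measurement before and one after training, a participant without the second value has no change score and adds nothing to the Group x Time test. The plan does not call its analysis completers-only, but the method makes it so.

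Completers of the four arms are comparable only if leaving is unrelated to outcome or works alike in every arm. The Metformin and Placebo paragraph of item 2a names gastrointestinal discomfort as the most common side effect, so unequal drop-out is plausible, although no rate by arm is given. If leaving also depends on the starting value, regression to the mean does the rest: an arm whose remaining members start higher shows a smaller average change, and one whose remaining members start lower shows a larger one, with no drug effect. A change score carries that imbalance into the result. At stake is a distorted metformin contrast, plus precision lost by ignoring a baseline that is already measured.

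**Working it through.** **1. The plan's own figure.** Taking both upper losses as shares of 120: 120 × (1 − 0.25 − 0.25) = 60, which matches the target. Taken in sequence, 120 × (1 − s) × (1 − d) runs from 67.5 (25%, 25%) to 86.7 (15%, 15%) and does not match.

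**2. How many randomised people have no post value.**
- If 15–25% applies to those randomised: 60/0.85 = 70.6, so 71, and 60/0.75 = 80. Then 11–20 are missing.
- On the reading that reproduces 60: 120 × 0.75 = 90 randomised and 30 lost, or 30/90 = 33%.

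**3. The ANOVA and the t-test are the same contrast.** With two groups and two time points, the Group x Time F equals the squared t on change. A numerical check gave 0.01057 for both. A person with no change score drops out of both.

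**4. Bias from baseline-related drop-out.** Assumptions that are not in the documents:
- 80 randomised in equal arms, pooled over drinks to 40 per side; two-sided 5% test; no true effect
- the same outcome SD before and after, pre–post correlation ρ of 0.5 or 0.8
- metformin loses 25%, with log-odds of leaving rising by b = 0.7 or 1.5 per SD of *lower* baseline; placebo loses 15% at random

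Completers number 40 × 0.75 = 30 and 40 × 0.85 = 34, so k = √(1/30 + 1/34) = 0.2505.

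Let δ be the mean baseline (in SD) of metformin completers, i.e. the mean of a standard normal z weighted by 1 − 1/(1 + exp(−(a − bz))), with a set to give 25% loss. Expected change falls by (1 − ρ) per SD of baseline. Hence bias = −(1 − ρ)δ, and the SE of the change contrast = k√(2(1 − ρ)). The error rate is Φ(−1.96 + x) + Φ(−1.96 − x), with x = |bias|/SE.

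| b | δ | ρ | Bias (SD) | SE (SD) | x | Error rate |
|---|---|---|---|---|---|---|
| 0.7 | 0.161 | 0.5 | −0.080 | 0.250 | 0.32 | 6.2% |
| 0.7 | 0.161 | 0.8 | −0.032 | 0.158 | 0.20 | 5.5% |
| 1.5 | 0.277 | 0.5 | −0.138 | 0.250 | 0.55 | 8.5% |
| 1.5 | 0.277 | 0.8 | −0.055 | 0.158 | 0.35 | 6.4% |

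Simulation under the same assumptions agrees: bias of about 0.03–0.14 SD and error rates of about 5–8.5%. The baseline-adjusted estimate stayed within 0.01 SD of zero.

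**5. Direction.** If higher-baseline people leave metformin instead, the sign reverses: +0.03 to +0.14 SD.

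**6. Same mechanism in both arms, still 25% versus 15%.** The bias is at most 0.05 SD, with an error rate of 4.6–5.4% in simulation.

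**7. Precision.** The adjusted SE is k√(1 − ρ²). At ρ = 0.5 it is 0.2505 × 0.866 = 0.217, against 0.250 for change scores. At ρ = 0.8 it is 0.2505 × 0.6 = 0.150, against 0.158. This gain does not need differential drop-out.

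**8. Where adjustment fails.** When metformin drop-out was made to depend on a poor *post-training* value, the adjusted estimate was off by +0.06 to +0.21 SD (error rate 6.5–17%), worse than change scores at +0.03 to +0.14 SD (5.0–8.2%).

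**The case against.** The strongest reply is that the bias is hypothetical. The documents give no drop-out by arm and no link between fitness and leaving. Discomfort is met with titration, dosing with meals and dose lowering, so it need not lead to withdrawal. A 15–25% rate alone biases nothing: equal rates and mechanisms in the arms leave the contrast unbiased. All of this stands, and it is why the size is given only under stated assumptions.

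A reader might infer that the plan is set up to produce a false finding that metformin blunts training, since Background, item 3a, raises that possibility. The documents do not support this. It needs low-baseline people to leave metformin in particular. The opposite selection flatters metformin or hides real blunting, and nothing shows which applies.

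A reader might also infer that baseline adjustment cures drop-out bias. Step 8 shows that it does not when leaving depends on the later response. Nor does a mixed model recover much from people who have only a baseline value. It offers nothing for isotope-based protein synthesis, which has no baseline although mitochondrial protein synthesis leads the purpose statement.

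Nor do the documents say that anyone is analysed outside the assigned arm, or that people who stop capsules are barred from post-training tests; on the latter they are silent. The Statistical Plan is written in the past tense, so visit conduct may no longer be open to change. The analysis still is.

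**Conclusion.** The concern holds in a limited form. For outcomes with a baseline, the planned tests use completers only and leave the baseline out as a covariate, while 11–20 of 71–80 randomised people are expected to have no post value (30 of 90 on the reading that reproduces the target). If drop-out differs by arm and depends on baseline, the bias is about 0.03–0.14 SD in either direction, with two-sided false positives of about 5–8.5%. Those figures rest on the assumed 25% versus 15% split, the slopes, the correlations, equal allocation and pooling over drinks; with one mechanism in both arms the bias nearly vanishes. The precision gain, about 0.22 against 0.25 SD at correlation 0.5, does not depend on the drop-out pattern. No direction of bias can be claimed from the documents, and the isotope outcome lies outside the remedy.

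**What to change.** - For each outcome with a baseline, replace the Group x Time ANOVA and the change t-test with ANCOVA on the post value, adjusted for baseline, or a mixed model with a common baseline mean across arms. Compare by assigned arm.
- Define the analysis set, and tabulate drop-out and reasons by arm.
- Use any available post-training assessments from people who stopped capsules or training, in their assigned arm.
- Add a sensitivity analysis that lets unobserved post-training values differ from the model's prediction, separately by arm. Adjustment does not cover drop-out related to the response and can make its bias larger.
- State that baseline adjustment cannot help the post-only isotope outcome, and apply the drop-out table and sensitivity analysis to it as well.

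The cost is a few sentences in the Statistical Plan and a standard regression or mixed-model routine on values already collected. Including people who stopped treatment may make the estimated effect slightly smaller.

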**1. Purpose of the study**

- a) Provide a brief lay summary of the project in <200 words. The lay summary should be readily understandable to the general public, and is, for example, what would be released to a newspaper if requested.

We propose that post-exercise milk protein feeding will enhance the mitochondrial protein synthesis (biogenesis) response to an exercise-training program. In addition, we propose that this stimulatory effect of protein feeding will overcome the potential blunting effect of metformin on exercise responses. We will investigate these outcomes over a 12-week exercise-training program in older adults with pre-diabetes with or without metformin treatment.

Sub-study:

- 1. CGM in Individuals with prediabetes undergoing an exercise-training program with or without Metformin.
- 2. CGM in healthy control individuals to compare to individuals with prediabetes.

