**b) What does the Investigator(s) hope to learn from the study?**

We hope to:

- a) provide the first evidence that post-exercise milk protein supplementation is effective in diseased population (i.e., older adults with pre-diabetes) and those on medications (i.e., metformin).
- b) demonstrate that the potential inhibitory effects of metformin on aerobic exercise adaptations can be opposed by milk protein feeding.

Sub-study

1. Glucose Profiles via CGM in pre diabetic individuals before, during and after the intervention (i.e., aerobic exercise training with or without metformin with post-exercise carbohydrate or carbohydrate+protein feeding as listed below in 2a).
- 2: Glucose profiles via CGM in healthy individuals. Healthy individuals will complete baseline procedures but will not complete an intervention.

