Pre diabetic and healthy participants will also have the option to participate in a study to wear a Dexcom generation 6 (G6) continuous glucose monitor (CGM) to measure glucose values every 5 minutes. Healthy participants will wear the device once for up to 10 consecutive days. Pre-diabetic participants will wear the device for up to 10-consecutive days at three different time points: before, during and after the 12-week exercise intervention for a total of 30 days wearing the CGM. The Dexcom G6 CGM is for investigational use only and is not FDA approved. The G6 is modeled after commercially available, FDA approved CGM devices. The differences between the G6 and commercially available devices are a reduced calibration scheme, meaning less finger stick blood glucose measurements for calibration; a longer wear for up to 10 days for the G6 vs. 7 days for commercially available product. Last, commercially available devices could give false high glucose readings if individuals took acetaminophen. The G6 sensor contains updated sensor technology aimed to block the interference of acetaminophen.

After randomization into placebo or metformin groups, the pre-diabetic subjects will begin a 12-wk exercise

intervention consisting of 3 days per week of aerobic exercise training with post-exercise consumption of a 20 gram protein beverage or isocaloric carbohydrate beverage. We have completed this supplementation protocol in previous studies and a currently ongoing investigation.

At the 8-wk time point, pre-diabetic subjects will begin the daily consumption of heavy water (D2O) for the assessment of mitochondrial and individual protein synthesis. At the completion of the training period, the pre-diabetic subjects will repeat all assessments performed prior to training including the DEXA, VO2max, OGTT and muscle sample. Muscle samples obtained pre- and post-training will be used to evaluate mitochondrial function using high-resolution respirometry, western blot analysis, and stable isotope incorporation (post only).

Healthy participants will complete the medical history questionnaire, resting ECG, graded exercise testing (ECG and VO2max), DEXA, OGTT, CGM, and muscle biopsy.

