**Identify inclusion criteria.**

We plan to recruit 120 men and women with an estimation that 15-25% of participants will not qualify (i.e., screen out) and 15-25% of participants will not complete the study (i.e. drop out). We plan to complete the study in 60 men and women aged >55 years who are prediabetic defined as impaired fasting glucose (100 to 126 mg/dl), HbA1c (5.7-6.4%), family history of type 2 diabetes, and/or impaired glucose tolerance defined as 2 hour postprandial blood glucose of 140 to 200 mg/dl. Participants will be eligible if they meet any 1 of these criteria.

10 healthy participants will be recruited who are 18-45 years old who have normal glucose values (fasting glucose <100mg/dl, HbA1c <5.7%, 2 hour postprandial blood glucose <140 mg/dl) and no family history of T2D.

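### Healthy controls (18-45) and prediabetic participants (over 55) share no ages, so any healthy-versus-prediabetic difference is confounded with age

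*Combined protocol and SAP*

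**What the plan says.** **Ages.** For the main population, Section 8(a) states: "We plan to complete the study in 60 men and women aged >55 years who are prediabetic". The healthy group in the same section is "10 healthy individuals, 18-45 years old who have normal glucose values". The inclusion criteria in Section 8(h) repeat the limit: "10 healthy participants will be recruited who are 18-45 years old". No reason is given for the younger range.

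**Purpose of the controls.** The sub-study list in Section 1(a) has "CGM in healthy control individuals to compare to individuals with prediabetes". Section 8(b) says "We will use a healthy control group to compare to individuals at risk for T2D", and Section 8(g) says "We will include healthy volunteers to compare to individuals at risk for T2D". The last two are not restricted to CGM.

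**What controls undergo.** Section 1(b): "Healthy individuals will complete baseline procedures but will not complete an intervention". Section 2(a) lists, besides CGM, an exercise test with VO2max, DEXA, an OGTT and a muscle biopsy. On CGM it adds "Healthy participants will wear the device once for up to 10 consecutive days". Prediabetic participants wear the device three times: before, during and after the intervention.

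**Sizes.** Section 8(a) plans 20 prediabetic and 10 healthy completers in the CGM sub-study, without a power calculation.

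**Control definition.** Section 8(a) joins normal glucose values and absence of family history with *or*. Section 8(h) joins them with *and*.

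**Analysis.** The Statistical Plan names a treatment-group by time ANOVA with repeated measures, Holm-Sidak post-hoc tests, an unpaired t-test on pre-to-post change, and Pearson correlation. It has no covariate and does not mention the healthy group.

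**The concern.** A control group is useful for this purpose only if it differs from the comparison group mainly in the condition of interest. Here the eligibility criteria make the groups differ completely in age as well. A CGM, VO2max, body-composition, OGTT or muscle difference could come from prediabetes, from age, or from both, and the data could not say which. This undermines the comparison for which the healthy group was added. The conflicting control definition blurs the contrast further: read literally, the *or* version admits a control with raised glucose.

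**Working it through.** **1. Overlap.** The oldest eligible control is 45 and the prediabetic group starts above 55. The gap between the closest possible pair is about 55 - 45 = 10 years (the exact minimum depends on whether ages are counted in completed years). No age can occur in both groups.

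**2. Anything that mitigates this.** The only matching statement, in the Study Overview of Section 2(a), concerns the randomised prediabetic arms. The ANOVA needs repeated measures and the t-test needs a pre-to-post change. Controls have one baseline assessment and one CGM wear, so neither test fits them. No age term appears.

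**3. The documents' own figure.** There is none to reproduce: no effect size, SD or power is given for 20 versus 10. For scale, with a two-sample t-test, two-sided 0.05 (sidedness assumed), 80% power and 28 df:
- standard error in SD units = √(1/10 + 1/20) = 0.387
- detectable difference = 1.12 SD by noncentral t (normal approximation (1.960 + 0.842) × 0.387 = 1.085)

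**4. Adding age as a covariate.** Assume ages uniform on 18-45 (mean 31.5) and on 55 to U, with U = 65 to 80. The variance of the group coefficient is multiplied by VIF = 1 + SSB/SSW for age, where SSB = (10 × 20/30) × gap² and SSW = 10 × 27²/12 + 20 × (U - 55)²/12.
- U = 65: gap 28.5; SSB = 5,415; SSW = 607.5 + 166.7 = 774.2; VIF = 7.99; detectable 1.124 × √7.99 = 3.18 SD
- U = 80: gap 36.0; SSB = 8,640; SSW = 607.5 + 1,041.7 = 1,649.2; VIF = 6.24; detectable 1.124 × √6.24 = 2.81 SD

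Simulated median VIFs over the same range of U were 8.68 down to 6.62 (detectable 3.31 down to 2.89 SD). With controls drawn from the same over-55 range, the median VIF was 1.02. Lost precision is the lesser problem. With no observations between 45 and 55, the adjusted estimate is valid only if the assumed age trend holds across that gap, and the data cannot test that.

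**5. Leaving age out.** Suppose prediabetes has no effect and the outcome drifts with age. The false difference is drift × gap/10, from 0.1 × 28.5/10 = 0.29 SD to 0.3 × 36/10 = 1.08 SD. The probability of P < 0.05 in an unpaired t-test of 20 versus 10 (noncentral t, 28 df) is:

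| Mean age gap (years) | Drift 0.1 SD/decade | 0.2 | 0.3 |
|---|---|---|---|
| 28.5 | 11.0% | 29.5% | 56.8% |
| 31.0 | 12.1% | 34.0% | 64.0% |
| 33.5 | 13.3% | 38.6% | 70.7% |
| 36.0 | 14.6% | 43.5% | 76.8% |

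The age distributions and the drift are assumptions. Only the age limits and group sizes come from the documents.

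**The case against.** The plan attaches no hypothesis, effect size or causal wording to the healthy group. Section 1(b) states the aim as glucose profiles in healthy individuals, and that descriptive aim stands. It does not dispose of the point, because Sections 1(a), 8(b) and 8(g) give comparison as the purpose and call the group a control group.

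The numerical illustration depends on chosen inputs. A reader might take the 11-77% false-positive range as a property of this trial. The documents do not support that: they give no age trend for any outcome, and the Statistical Plan does not specify the baseline t-test behind those rates. The confounding itself follows from the age limits alone.

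A reader might also infer that no analysis of this comparison was ever planned. Section 16 lists a CGM SOP, a GCP protocol and a CGM proposal that are not reproduced, and any of them could contain one. No analysis, however, can supply the age overlap that eligibility excludes.

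A further tempting inference is that the trial's main result is compromised. It is not: the four arms are randomised within the prediabetic group, and controls do not enter that comparison. Confining the problem to CGM would be the opposite mistake, since controls also have VO2max, DEXA, OGTT and biopsy measurements.

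Finally, changing the age range may come too late. The healthy-volunteer consent is dated 11 July 2017, the October 2018 amendment summarises only a change of principal investigator, and the Statistical Plan is in the past tense. This suggests that controls were enrolled but does not prove it, so the fix has to cover both cases.

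**Conclusion.** The point holds. Every healthy-versus-prediabetic contrast, in CGM or in the other baseline measures, is confounded with age, and a covariate cannot undo it. What the documents establish is a gap of about 10 years between the closest possible participants, with 10 controls against 20 prediabetic participants for CGM. Under the assumed uniform ages the mean gap is 28.5-36 years, and age adjustment raises the detectable difference from 1.12 SD to about 2.8-3.3 SD. The size of any actual age bias is unknown. The randomised comparison and a description of young healthy profiles are untouched. The *or*/*and* conflict is a separate documentary contradiction. It may be a slip, but as written the two sections define different control groups.

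**What to change.** **1. Age.**
- *Controls not yet enrolled:* change their age range in Sections 8(a) and 8(h) to overlap the prediabetic group (over 55). Add a line to the Statistical Plan comparing the controls' single CGM wear with only the pre-intervention wear of the prediabetic participants, with age as a covariate. The restriction keeps exercise and drug effects out of the contrast. Cost: people over 55 with normal glucose may take longer to recruit.
- *Controls aged 18-45 already enrolled:* report them descriptively as a young reference group beside the pre-intervention prediabetic values, with no formal test and no claim that a difference is due to prediabetes. Apply the same label to VO2max, DEXA, OGTT and biopsy results. Cost: wording only, and the loss of a conclusion that the data could not support.

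**2. Control definition.** Reconcile Sections 8(a) and 8(h) so that a control with raised glucose cannot be counted as healthy, and report the glucose values of any control who meets only one part of the definition. Cost: a wording change in one section and a short listing.

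**Optional, and separate from age.** Family history alone qualifies a participant as prediabetic, so the summary could be repeated in those who meet a glycaemic criterion. If an assumed 10-50% of the 20 qualify on family history alone, 18 to 10 remain. If a test were used, its detectable difference against 10 controls would rise from 1.12 SD to 1.15-1.32 SD.
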